- Design Overview.** For *Aim 1*, up to 150 participants with HBR on DAPT with clopidogrel and aspirin, who have undergone successful PCI will be stratified by the *CYP2C19* LOF allele within one week of DAPT initiation. If present, participants will be given prasugrel or ticagrelor monotherapy, and non-carriers will continue with clopidogrel monotherapy. The primary safety endpoint will be a composite of post-dismissal cardiac death/spontaneous MI <30 days or stent thrombosis <90 days of discharge. For *Aim 2*, the same subjects will undergo post-dismissal assessment for BARC 3 or 5 bleeding, all-cause death, any MI, and/or repeat revascularization up to 180 days. Informed consent followed by genotype assessment will be obtained prior to discharge. Loading dose of clopidogrel (600 mg) will be given to all patients and maintenance dose of 75 mg daily will be given, as indicated. We will allow patients to be given loading dose (324 mg) of aspirin either before or at the time of PCI. The choice of stents, access site and treatment site will be at the discretion of the treating physician (**Figure 1**).
- Clopidogrel and prasugrel/ticagrelor administration.** This study will be single-center, single-arm, open label, first-in-human, and a proof-of-concept, pilot and safety study. All participants in the first week will receive clopidogrel bolus (600 mg) and maintenance (75 mg) and aspirin bolus (324 mg, if not on aspirin) and 81mg maintenance. Participants with HBR who meet the inclusion criteria will be stratified by *CYP2C19* LOF allele. Non-carriers (or those with inconclusive results) will continue with maintenance dose of clopidogrel monotherapy at 75 mg daily. If LOF allele is present, they will be prescribed either prasugrel or ticagrelor monotherapy [prasugrel 60 mg load, maintenance 10 mg daily; ticagrelor 180 mg load, maintenance 90 mg twice daily; dose escalation with bolus regardless of timing of the last clopidogrel dose]. Prasugrel will be the preferred agent except when absolutely contraindicated (history of stroke/transient ischemic attack or active bleeding). Patients ≥ 75 years or < 60 kg will receive prasugrel at a reduced dose of 5 mg daily. If there is

Figure 1: Study Flow Chart

a relative contraindication to prasugrel (as determined by the treating physician), the participant will be given ticagrelor. Maintenance aspirin will be discontinued in both arms once genotype testing has been confirmed. (**Figure 1**).

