- Hemoglobin at time of bleeding event (obtain from chart review; not available in registry)
- Creatinine and eGFR at time of PCI
- Use of clopidogrel, prasugrel, ticagrelor
- Use of oral anticoagulant (warfarin, apixaban, rivaroxaban)

Aim 1: Detailed Approach

The objective of aim 1 is to determine if clopidogrel monotherapy following successful PCI is safe among non-carriers of CYP2C19 LOF allele. The hypothesis is that carriers of CYP2C19 LOF genotype are unable to metabolize clopidogrel effectively to an active drug that blocks P2Y12 receptors and inhibit platelet aggregation and are therefore at heightened ischemic risk following PCI. We will reduce bleeding risk by giving clopidogrel monotherapy only to non-carriers. Our approach to test this hypothesis is stratifying HBR patients after successful PCI into those with CYP2C19 LOF allele and those with inconclusive results or who are

| Schedule of Events | Day 0 | Day 1 | Day 2 | Day 3 | Day 4 | Day 5 | Day 6 | Day 7 ± 2 days | Day 30 ± 1 week | Day 90 ± 1 week |
|--|-------|-------|------------|-------|-------|-------|-------|-------------------|--------------------|--------------------|
| Stent Placement | ■ | | | | | | | | | |
| Informed Consent | | ■■■ | | | | | | | | |
| Genotype Test Blood Draw | | ■■■■ | | | | | | | | |
| Study Coordinator Call with Genotype Results & Final Medication Decision | | | ■■■■■ | | | | | | | |
| Stop aspirin and continue clopidogrel or change to prasugrel/ticagrelor | | | ■■■■■■■■■■ | | | | | | | |
| 1 st Study Coordinator Follow Up Call | | | | | | | | ■ | | |
| 2 nd Study Coordinator Follow Up Call | | | | | | | | | ■ | |
| 3 rd Study Coordinator Follow Up Call | | | | | | | | | | ■ |

non-carriers. Within first week of DAPT initiation, non-carriers will receive clopidogrel monotherapy, and prasugrel/ticagrelor will be given to patients with CYP2C19 LOF allele. The *rationale* for this aim is to individualize antiplatelet therapy and to reduce bleeding risk by stratifying P2Y12 pharmacotherapy by the CYP2C19 LOF genotype. Large number (50%-70%) of patients are non-carriers and in them clopidogrel monotherapy would suffice and the remainder will receive prasugrel or ticagrelor thereby lowering bleeding risk, cost, and unique adverse effects related to ticagrelor (e.g., bradycardia, dyspnea) or excess bleeding related to prasugrel. Recruitment should not be a challenge at Mayo Clinic, Rochester where 30% of PCI patients are HBR.

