Background. The highest risk for readmissions for bleeding is within 30 days of discharge, and those with PDB are also at heightened ischemic risk for death/MI within the first 60 days of bleeding-related hospitalization. These findings suggest a critical period after bleeding events when patients are most vulnerable for further adverse events. Contemporary studies have abbreviated the DAPT duration (1-3 months) or have deescalated the intensity of P2Y12 inhibitors only after this critical period is over. There is an urgent need to test early antiplatelet deescalation leveraging CYP2C19-LOF allele-based stratification.

Preliminary Studies. HBR patients represent 30%

of all patients who underwent PCI in the Mayo Clinic, Rochester catheterization laboratory between January 2010 and July 2021. Role of genotyping in reducing the incidence of major bleeding following PCI: TAILOR PCI

demonstrated a 34% risk reduction of ischemic events (HR 0.66, 95% CI 0.43-1.02, p=0.06) at 12 months with genotype guided P2Y12 inhibitor therapy.²⁰ Importantly in that trial, a post-hoc analysis demonstrated an almost 80% risk reduction (p=0.001) for ischemic events with genotype guidance in the first 3 months after PCI, the highest risk period following PCI. A recent meta-analysis using data from 7 randomized control trials with

15,949 patients demonstrates a 30% risk reduction in ischemic events (95% CI 0.59-0.83) in CYP2C19LOF allele patients with the use of ticagrelor/prasugrel vs clopidogrel and a RR of 1.0 (95% CI 0.80-1.25) in wild-type or no LOF patients indicating that CYP2C19 genotype played a significant role in driving the benefit of ticagrelor/prasugrel.²⁵

Research Design

1. **Assessment of high bleeding risk:** Academic Research Consortium (ARC) defined 1-year high bleeding risk as a BARC 3 or 5 risk of $\geq 4\%$ or a risk of intracranial hemorrhage of $\geq 1\%$.²⁶ The variables included in this risk model are listed in **Table 1**. Twenty clinical criteria were chosen as major or minor, and patients are at high risk for bleeding if at least 1 major or 2 minor risk criteria are met. This model successfully identified high bleeding risk patients following PCI.²⁷

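### Aim 1 names a hypothesis about LOF carriers on clopidogrel that the design cannot test, because identified carriers are switched to another drug; the sentence also conflicts with the aim's other statements of purpose

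*Combined protocol and SAP*

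**What the plan says.** Aim 1: Detailed Approach contains four statements that have to be read together.

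- Objective: "The objective of aim 1 is to determine if clopidogrel monotherapy following successful PCI is safe among non-carriers of CYP2C19 LOF allele".
- Hypothesis: "The hypothesis is that carriers of CYP2C19 LOF genotype are unable to metabolize clopidogrel effectively to an active drug that blocks P2Y12 receptors", from which the text concludes that carriers have a raised ischemic risk after PCI.
- Test: "Our approach to test this hypothesis is stratifying HBR patients after successful PCI into those with CYP2C19 LOF allele and those with inconclusive results" or a non-carrier genotype.
- Treatment: "non-carriers will receive clopidogrel monotherapy, and prasugrel/ticagrelor will be given to patients with CYP2C19 LOF allele".

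The section on drug administration describes the design: "This study will be single-center, single-arm, open label, first-in-human, and a proof-of-concept, pilot and safety study". It keeps inconclusive results on clopidogrel with the non-carriers.

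Two other places state the purpose differently. Specific Aim 1, at the front of the protocol, gives the hypothesis as the safety of clopidogrel monotherapy in 100 HBR patients. It makes the primary safety endpoint a noninferiority statement about clopidogrel monotherapy, stratified by LOF status. Expected Outcomes, under Aim 1, asks whether non-carriers on clopidogrel monotherapy have increased ischemic risk.

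**The concern.** The hypothesis in the detailed approach concerns what happens to carriers when they take clopidogrel. The design then removes identified carriers from clopidogrel. Stratifying by genotype cannot test the statement, because the stratum it describes is no longer on the drug it describes.

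What is at stake is the reading of the results. Stratum-specific rates are likely to be reported, since the endpoint is stratified by LOF status, and the text invites the reader to treat them as a test. Similar rates could be taken as evidence against the metabolism premise, and a higher carrier rate as evidence for it. Neither inference would be sound. A second problem is that the aim has three non-matching statements of purpose, so it is unclear which result would answer it.

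**Working it through.** The documents as supplied give no margin, significance level, power or test for a genotype contrast, so there is no figure to reproduce. The check is one of identifiability.

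**1. Which combinations of genotype and drug are observed after the switch** (Specific Aim 1; drug administration section; Aim 1: Detailed Approach)

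| Genotype result | Clopidogrel monotherapy | Prasugrel or ticagrelor |
|---|---|---|
| Confirmed non-carrier | all, by rule | none planned |
| Inconclusive | all, by rule | none planned |
| Identified carrier | none planned | all, by rule |

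The hypothesis compares carriers with non-carriers, both on clopidogrel. The carrier cell it needs is empty by plan.

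**2. What the strata can show.** Let p be the event risk of non-carriers on clopidogrel, r the risk ratio of carriers to non-carriers if both took clopidogrel, and s the risk ratio in carriers of the potent drug to clopidogrel. The hypothesis is r > 1. Then:

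- observed non-carrier risk = p
- observed carrier risk = p × r × s
- observed ratio k = r × s

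There is one observed ratio and two unknowns. For any k, every s > 0 has a matching r = k/s. For example, k = 1 arises if r = 1 and s = 1 (hypothesis false), and also for any r > 1 with s = 1/r (hypothesis true). More patients sharpen k but do not separate r from s.

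**3. Whether anything else in the plan supplies r**

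- *First week.* All participants take clopidogrel with aspirin, so carriers have some clopidogrel exposure. It is dual therapy, part of it precedes discharge while the endpoint counts post-dismissal events, and no analysis of the window is described. Events would also be few. Inputs: 100 to 150 patients; 30% to 50% carriers (from the stated 50% to 70% non-carriers); 30-day death or MI of 5% (2017) to 9% (all years), from Table 2; and an assumed 25% to 50% of 30-day events falling in week 1, a share the documents do not give. Expected carrier events without excess risk run from 100 × 0.30 × 0.05 × 0.25 = 0.4 to 150 × 0.50 × 0.09 × 0.50 = 3.4. Table 2 counts death or MI, not the primary composite, so this is only an order of magnitude.
- *Inconclusive results.* These patients stay on clopidogrel and may include carriers, but their genotype is unknown. The switch rule names `*2` and `*3`, while the allele list in the assay section does not show `*3`. Any carrier missed for that reason would be unidentified and equally uninformative.
- *Registry cohort.* It is on standard DAPT, and genotype is not among the items listed for capture under Control Cohort.
- *Laboratory evidence.* No platelet-function or metabolite measurement is described, so the metabolism claim is not tested directly either.

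**4. The stratified endpoint in Specific Aim 1.** At 30% to 50% carriers, the carrier stratum is 30 to 50 of 100 active patients (45 to 75 of 150). That stratum is assigned prasugrel or ticagrelor, so its event rate cannot be a result about clopidogrel monotherapy.

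**The case against.** The strongest reply is that the sentence is a pharmacological premise, mislabelled. Specific Aim 1 gives the formal hypothesis, and both the objective and Expected Outcomes concern non-carriers. This largely stands: the sentence works as background and the non-carrier question remains addressable. But the text calls it the hypothesis, says it will be tested, and sets out a rationale separately in the same section, so the mismatch is real.

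It is also fair that no section specifies a carrier versus non-carrier test or says how stratum rates would be interpreted. The comparator described is the registry cohort. The misreadings above are therefore a risk that the wording creates, not an analysis the protocol has committed to.

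An absolute claim that no carrier is ever observed on clopidogrel would go too far. Besides the first-week exposure, aspirin is stopped once results are available while the replacement drug is sent by mail. As written, a carrier could briefly be on clopidogrel alone. None of this yields a usable test.

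A reader might also infer from the meta-analysis under Preliminary Studies that equal stratum rates are the signature of a true hypothesis. The documents do not support that. The 30% reduction compares drugs within carriers, and "a RR of 1.0 (95% CI 0.80-1.25) in wild-type or no LOF patients" compares drugs within non-carriers. Neither gives carrier versus non-carrier risk on clopidogrel. Setting that risk to the inverse of the drug effect assumes the answer, and equal rates arise when the hypothesis is false as well.

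**Conclusion.** The point holds as a mismatch between hypothesis, approach and objective: wrong as written, moderate severity. The hypothesis about carriers is not identifiable from the planned data. This rests only on three features of the plan: a single arm, drug assigned by genotype, and no genotyped comparison group on clopidogrel. It does not depend on any assumed event rate or risk ratio. The first-week event count does rest on assumptions, and serves only to show that this window is no substitute.

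Two stronger conclusions would be unwarranted. Aim 1 as a whole is not untestable, since incidence in patients assigned to clopidogrel monotherapy can be estimated. Nor is genotype-guided assignment a design flaw; it is the strategy under study. What has to go is the claim that this assignment tests the metabolism premise, together with the endpoint wording that attaches clopidogrel monotherapy to a stratum assigned another drug.

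**What to change.** 1. In Aim 1: Detailed Approach, move the metabolism statement to the rationale and delete the claim that stratification tests it.
2. In Specific Aim 1 and in Aim 1: Detailed Approach, state one target: incidence of the primary composite (a) in patients assigned to clopidogrel monotherapy, meaning non-carriers plus inconclusive results, with confirmed non-carriers also shown separately; and (b) in all patients under the genotype-guided strategy. Give each with an exact confidence interval. This replaces the noninferiority wording stratified by LOF status.
3. Add that any carrier versus non-carrier difference is descriptive and will not be read as an effect of genotype or of drug.
4. Reconcile the alleles named in the switch rule with those in the assay list, so that membership of the confirmed non-carrier group is well defined.

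The inconclusive results stay in group (a) because the protocol treats them with the non-carriers. The separate display shows whether they alter the result.

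Items 1 to 3 cost wording only: enrollment, treatment, endpoint components and data collection are unchanged. The trial gives up a claim it could not have supported.

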Specific Aim 1: Test the hypothesis that clopidogrel monotherapy is safe following successful PCI among 100 consecutive patients with HBR and meeting the inclusion criteria (100 *active* patients, excluding patients who have been enrolled then withdrawn for various reasons such as starting an additional blood thinner, patient preference, etc.). To ensure that we have data on 100 active patients that complete their 1 month visit, we will plan to accrue up to 150 patients. The primary safety end point will be showing noninferiority of clopidogrel monotherapy in reducing ischemic events stratified by presence or absence of *CYP2C19* LOF allele (QuantStudio with Chemagic DNA extraction). All patients will receive clopidogrel (600 mg load & 75 mg maintenance) and aspirin (324 mg load & 81 mg maintenance) for the first week. Those with *CYP2C19* 2* or 3* LOF allele (*CYP2C19* LOF carriers) will be prescribed prasugrel or ticagrelor [prasugrel 60 mg load, maintenance 10 mg or 5 mg (for patients \geq 75 years or $<$ 60 kg) daily or ticagrelor 180 mg load, maintenance 90 mg twice daily (dose escalation with bolus will occur regardless of the timing of the last clopidogrel dose)]. Non-carriers (or those with inconclusive results) will continue with clopidogrel 75 mg daily maintenance dose. Aspirin will be stopped in all patients once *CYP2C19* results are available.

Specific Aim 2: Among participants enrolled in aim 1, aim 2 will determine the incidence of BARC 3 or 5 bleeding events. Other secondary endpoints are post-dismissal all-cause death, any MI up to 180 days, repeat revascularization, or any other BARC bleeding episodes.

SIGNIFICANCE

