 - c) **Subject Accrual Plan:** The recruitment will be drawn from the Earl Wood Cardiac Catheterization Laboratory (>1,500 PCIs/year) and Cardiology inpatient services at St. Mary's Hospital. Day 1 will include screening following successful PCI, bleeding risk calculation (ARC-HBR), enrollment, informed consent, and clinical CYP2C19 assay collection. On day 30, a study coordinator phone call will occur to assess ischemic symptoms, readmission, and bleeding. On day 90, a study coordinator phone call will again assess ischemic symptoms, readmissions, and bleeding. All encounters will include drug education and assurance of compliance.
 - d) **Reassessment:** The study coordinator will make phone calls at one and three months to inquire about ischemic symptoms, readmissions at other hospitals with MI, or any bleeding.
7. **Control Cohort:** A cohort of similar patients will be identified from the Mayo Clinic catheterization laboratory PCI registry to determine rates of ischemic and bleeding events in a cohort of HBR post-PCI patients receiving standard of care DAPT after PCI. These patients will be identified by registry review, and we will utilize ICD diagnosis codes to identify bleeding and ischemic events. Retrospective chart review will verify the clinical situation to ensure the validity of the coded diagnoses (to minimize errors inherent to diagnosis coding). There will be no direct patient contact, and patients who refused registry research participation will be excluded from this study. We aim to obtain the following

data:

A. Events

- Event type (category below); diagnosis codes selected from Mayo Clinic database of ICD codes (<https://intranet.mayo.edu/charlie/quantitative-health-sciences-groups/rochester-epidemiology-project/index-of-possible-codes-for-specific-conditions-diseases/>)
- Date of ischemic/bleeding event
- Bleeding Categories
 - *Hemorrhage, gastrointestinal*
 - *Stroke (hemorrhagic)*
 - *Disease, cerebrovascular (hemorrhagic)*
 - *Hematuria*
- Ischemic Categories
 - *Infarction, myocardial*
 - *Disease, cerebrovascular (TIA, ischemic stroke)*

B. Inclusion

- Successful PCI
- Approx. 1 year date range TBD (n = 1500 patients; targeting contemporary PCI patients within the last 2 years).

C. Exclusion

- Enrolled in CHAMP Trial

D. Demographic/Procedure Info to Capture from PCI Registry

- Age/DOB
- Sex
- Race
- Event type (STEMI, NSTEMI/unstable angina, chronic CAD)
- PCI date
- Hemoglobin at time of PCI

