2. **Assessment of CYP2C19LOF Allele:** Clinical CYP2C19 assay will be run on QuantStudio with Chemagic DNA extraction that assesses CYP2C19 (*2, *10, *17, *35) The results will be expected within 72 hours of receipt of the samples. Once received, the results will be communicated to the participants and clopidogrel monotherapy will be initiated or samples of prasugrel or ticagrelor will be mailed.

Expected Outcomes. From these data, we will determine whether there is increased ischemic risk in HBR non-carriers of CYP2C19 LOF genotype receiving clopidogrel monotherapy post-PCI. Close monitoring of participants receiving clopidogrel monotherapy or prasugrel/ticagrelor monotherapy for any cardiac deaths, spontaneous MI and stent thrombosis will be done.

Potential Problems and Alternative Strategies. The results of genotype-based assay will be available at or following the participant's discharge. To ensure compliance with clopidogrel monotherapy or switch among participants with CYP2C19 LOF allele, the study coordinator will call them with the results, mail the 90-day prescription for prasugrel or ticagrelor and ensure its receipt and initiation. Based on the expert consensus, pharmacodynamic data, escalation in patients with *CYP2C19 2* or 3*LOF allele* will require stopping clopidogrel and switching to 60 mg loading dose of prasugrel or 180 mg loading dose of ticagrelor regardless of the timing of the last dose of clopidogrel followed by standard maintenance dose of prasugrel 10 mg daily (5 mg if age ≥ 75 years or weight < 60 kg) or ticagrelor 90 mg twice daily. We have elected to exclude patients on chronic warfarin or DOAC. While this is an ARC major criterion for HBR, aspirin is already being discontinued frequently post-PCI in many patients to avoid triple therapy, and we want to ensure that this study is truly evaluating antiplatelet monotherapy and is not confounded by use of chronic anticoagulants. Patient enrollment is another potential problem, but our group has a strong track record of successfully enrolling participants into

Table 1: Criteria for High Bleeding Risk at the Time of Percutaneous Coronary Intervention

| Major | Minor |
|---|---|
| | Age ≥ 75 years |
| Anticipated use of long-term oral anticoagulation | |
| Severe or end-stage chronic kidney disease (eGFR <30 mL/min) | Moderate chronic kidney disease (eGFR 30 to 59 mL/min) |
| Hemoglobin <11 g/dL | Hemoglobin 11.0 to 12.9 g/dL for men and 11.0 to 11.9 g/dL for women |

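### The allele list and the aspirin-stop rule each need one clarification so that no CYP2C19 loss-of-function carrier is left on clopidogrel alone

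*Combined protocol and SAP*

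**What the plan says.** **Alleles.** The assay description (Aim 1, Research Design, item 2) reads: "Clinical CYP2C19 assay will be run on QuantStudio with Chemagic DNA extraction that assesses CYP2C19 (*2, *10, *17, *35". No other panel is given. Specific Aim 1 defines the carriers to be switched as those with a "2* or 3* LOF allele". The Aim 1 section on potential problems repeats those two alleles and says that escalation "will require stopping clopidogrel and switching to 60 mg loading dose of prasugrel or 180 mg loading dose of ticagrelor". General Methods item 2 is broader: "If LOF allele is present, they will be prescribed either prasugrel or ticagrelor monotherapy". Anyone not identified as a carrier, or whose result is inconclusive, stays on clopidogrel.

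**Aspirin.** Specific Aim 1 gives every patient clopidogrel plus "aspirin (324 mg load & 81 mg maintenance) for the first week". The same paragraph also says "Aspirin will be stopped in all patients once" the genotype result is available, and General Methods item 2 repeats this: "Maintenance aspirin will be discontinued in both arms once genotype testing has been confirmed".

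**Supply and timing.** Day 1 includes "enrollment, informed consent, and clinical CYP2C19 assay collection" (item 6c, Subject Accrual Plan). Results are expected within 72 hours of sample receipt and become known at or after discharge. The coordinator then mails prasugrel or ticagrelor to carriers, confirms that it has arrived and tells them to take the loading dose (General Methods item 3; Aim 1, Research Design item 2 and potential problems). The Aim 1 Detailed Approach places the start of the new drug within the first week of dual therapy. It also reserves clopidogrel monotherapy for non-carriers.

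**The concern.** The Detailed Approach holds that LOF carriers cannot activate clopidogrel effectively and so face a higher ischemic risk. Two pieces of wording, followed as printed, could put a carrier on clopidogrel alone.

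- **An allele acted on but not listed as tested.** A broad rule about any LOF allele cannot reach one that the assay does not report. A \*3-only patient would remain on clopidogrel alone for the whole treatment period and be counted in the non-carrier stratum.
- **Aspirin stopped by the result rather than by the switch.** If aspirin ends when the result is known and the replacement is still in the mail, a carrier has only clopidogrel in the meantime. This gap is temporary, and the patient stays in the carrier stratum, so it concerns treatment sequence and does not bias the non-carrier estimate.

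The section on reducing ischemic hazard says that MI-related cardiac death predominates during the first week after PCI and that the risk of death stays fairly high for two weeks. Patients with acute coronary syndrome are eligible. Any gap would fall in that period.

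**Working it through.** The plan states no figure for either point, so there is none to reproduce. The check sets the rules side by side and adds simple arithmetic.

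**1. Allele lists**

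- Tested, as printed: \*2, \*10, \*17, \*35.
- Acted on: \*2, \*3.
- Acted on but not listed as tested: \*3. A \*2/\*3 patient is still found through \*2; a \*3-only patient is not.

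The plan gives no \*3 frequency. For scale only, assume that 0.1–5% of patients carry \*3 as their sole LOF allele:

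- Missed carriers: 0.1–5 of 100, or 0.15–7.5 of 150.
- Baseline risk: Table 2 gives 6–7% death or MI at 90 days for 2016–2017. This differs from the primary endpoint, and the table is not stated to be limited to high-bleeding-risk patients.
- Relative reduction: the Aim 1 Preliminary Studies cite 30% to almost 80%, assumed here to carry over to monotherapy.
- Excess risk per missed carrier = baseline × relative reduction: 6% × 0.30 = 1.8 points, up to 7% × 0.80 = 5.6 points.
- Excess events per 100 enrolled: 0.1 × 0.018 = 0.002, up to 5 × 0.056 = 0.28.
- Excess events per 150 enrolled: 0.15 × 0.018 = 0.003, up to 7.5 × 0.056 = 0.42.
- With Table 2's all-years 90-day figure of 12%, the upper ends become 5 × 0.12 × 0.80 = 0.48 per 100 and 7.5 × 0.12 × 0.80 = 0.72 per 150.

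The expected excess is below one event in each of these cases.

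**2. Aspirin and the switch**

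- Carriers = 1 − non-carrier share. At 50–70% non-carriers (Aim 1 Detailed Approach), that is 30–50 of 100 active patients, or 45–75 of 150. At 60–70% (Aim 2 Background), it is 30–40 of 100, or 45–60 of 150.
- Result day: Day 1 sample + 72 hours = Day 4, assuming receipt on the day of sampling.
- Latest start of the new drug under the Detailed Approach: within the first week, taken as Day 7.
- Gap if aspirin stops at the result: at most 7 − 4 = 3 days per carrier.
- Total per 100 patients: 30 × 3 = 90 to 50 × 3 = 150 patient-days if every carrier waits until Day 7. Faster delivery, or a result already known at discharge, lowers this. Each day by which the result precedes Day 4 could add up to 50 × 1 = 50 patient-days.
- Gap if aspirin runs through the first week and the new drug starts within it: 0 days.
- Gap if aspirin continues until loading: 0 days by construction.

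The documents give no basis for estimating excess events during such a gap.

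**The case against.** The strongest reply is that the plan can be read so that neither problem arises.

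- **Sequence.** Aspirin through the first week, combined with the new drug inside that week, leaves no gap. The schedule of events puts the aspirin stop and the drug change in one row, separate from the results call. The coordinator must see that the drug arrives and is started, and monotherapy with clopidogrel is meant only for non-carriers. Figure 1 is cited directly after an aspirin-stop sentence and is not visible in the text available here, so it may settle the order. These points stand as evidence of likely intent. They do not remove the two sentences that tie the stop to the result for everyone, and no text shown says what a carrier takes until the loading dose.
- **Allele list.** Star alleles are printed irregularly in this document, so the panel may be mistyped or badly extracted. That stands, and it is why the first step is to confirm what the assay reports.
- **Inconclusive results.** The plan already keeps these patients on clopidogrel, so it accepts some unidentified carriers. True, but that is a declared choice. A \*3-only patient would be labelled a non-carrier against the plan's own definition.
- **Protection.** Thrombus and high-risk lesions are excluded, the DSMB reviews data during enrollment, and the plan describes early stent thrombosis as uncommon with current stents. These lessen the concern.

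A reader might infer a longer gap by assuming slow mail, for example loading on Day 9. The first-week sentence in the Detailed Approach does not support that. A reader might also take the first week to be named as the period of highest risk. The ischemic-hazard section does not say so, and the Aim 1 Preliminary Studies use that description for the first three months.

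**Conclusion.** Both points hold as inconsistencies in the printed text, and together they are a minor to moderate safety clarification.

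On alleles, \*3 is acted on but absent from the only listed panel. The number of patients affected cannot be derived. With an assumed \*3-only share of 0.1–5%, the expected excess is below one event. The documents do not show that the assay fails to report \*3, so no one should conclude that carriers are in fact being missed, or that the non-carrier estimate would shift materially.

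On aspirin, the two end points conflict. One reading leaves no gap. The stop-at-result reading allows 30–50 carriers per 100 up to about 3 days on clopidogrel alone, at most about 150 patient-days per 100. That figure rests on a Day 4 result and on the new drug starting by Day 7. The plan does not instruct that carriers go unprotected; its wording permits a gap that its own rationale would rule out. Sample size and power are not affected.

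**What to change.** 1. Confirm with the laboratory whether the assay reports \*3. Use a single list for alleles tested and alleles acted on in Specific Aim 1, the assay description and the escalation rule. If \*3 is not reported, amend the carrier definition or use a panel that includes it.
2. In Specific Aim 1, General Methods items 2 and 3, the assay description and the Aim 1 potential-problems text, state that non-carriers stop aspirin at the result and that carriers continue it until the prasugrel or ticagrelor loading dose has been taken. Check that Figure 1 and the schedule row agree.
3. Record the date of the last aspirin dose and the date of loading on the case report form, so that any gap can be measured. The plan describes a pill count at 3 months but neither of these dates.

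The cost is a protocol clarification and two data fields. The clinical downside is a few more days of dual therapy in high-bleeding-risk carriers, largely within the week already planned.
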